5.2 Analysis of Baseline Data and Exposure to Study Drug

The baseline data and exposure to study drug will be summarized for pharmacodynamic population. Descriptive statistics will be presented for both continuous endpoints and categorical endpoints.

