5 STATISTICAL ANALYSIS METHODS

5.1 General consideration

The statistical software, SAS[®], will be used for all summaries and statistical analyses.

This study only includes a single arm. In general, statistical analyses will be descriptive in nature with appropriate measures of variation provided where applicable. For continuous endpoints, number of subjects in the analysis population, number of subjects with non-missing observations, mean, standard deviation (SD), median, minimum and maximum will be reported. For categorical endpoints, number of subjects in the analysis population, number with non-missing observations, and the percent of those with data in each category will be summarized.

Several analysis populations are defined for different analysis purposes in this study. An overview of these analysis populations will be summarized.

- Pharmacodynamic Population - it is defined as all subjects who receive at least 1 dose of study treatment and have at least 1 pharmacodynamic measurement after Baseline.

CONFIDENTIAL

The information contained herein may not be used, disclosed, or published without the written consent of Biogen Idec MA Inc.

	Protocol 109MS310 An Open-Label Study to Assess the Effects of BG00012 on Lymphocyte Subsets in Subjects With RRMS	Final Version 1.0
---	---	--------------------------

- Safety Population – it is defined as all subjects who receive at least 1 dose of study treatment.

- [REDACTED]

[REDACTED]

In general, for data that are summarized by visit, any early withdrawal, unscheduled or scheduled visits will be assigned to an appropriate scheduled visit by using a mid-point of the two visits windowing scheme. The date of first dose will be the reference point. The detailed windowing rules for lymphocyte subsets, hematology, blood chemistry and vital signs are available in [Appendix 2](#). After windowing, if there is only 1 record in the visit window, then this record will be selected; if there are multiple records falling into the same visit window with different distance from the target day then select the one closest to the target day; if there are 2 visits with the same distance from the target day, but one is before the target day and the other is after the target day, then select the later one; for laboratory test, if more than one observation falls in the same distance from the target regular scheduled visit day, the mean observation will be calculated and used in the summary statistics and analyses.

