5.2.1 Accounting of Subjects

Numbers and percentages of subjects enrolled, completed the treatment, and completed the study, along with reasons for discontinuing treatment and withdrawing from the study, will be presented.

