5.2.5 Time on Study and Treatment

The total number of days/weeks patients on study will be summarized. Number of weeks the subject on the study will also be categorized into 12 week intervals and summarized. The total number of days subjects on study is calculated as

$$\text{Date of study end} - \text{date of first dose} + 1.$$

The total number of days/weeks patients on treatment will be summarized. Number of weeks the subject on treatment will also be categorized into 12 week intervals and summarized.

The time patients on temporary drug interruption will be excluded from the time on treatment calculation. Therefore, the total number of days subjects on treatment is calculated as

$$(\text{Date of last dose} - \text{date of first dose} + 1) - \text{total days of temporary dose interruption if any.}$$

For partial study or study treatment end date, if day is missing then impute the day to 30/31/28/29 depending on the month; if day and month are missing then impute the month and day to December 31st.

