5.4 Safety

All AEs, clinical laboratory results, physical examinations, vital signs, and 12-lead ECG readings data will be evaluated for safety. The data from safety population defined in [Section 5.1](#) will be used for safety analysis. Statistical analyses will be [REDACTED] and descriptive in nature.

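### SAP 5.2 summarises exposure on the pharmacodynamic population while adverse events use the safety population, so a dosed subject with no post-baseline sample appears in one set of tables and not the other

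*SAP*

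**What the plan says.** The opening sentence of SAP 5.2 assigns the population for the section: "The baseline data and exposure to study drug will be summarized for pharmacodynamic population". SAP 5.1 defines that population as "all subjects who receive at least 1 dose of study treatment and have at least 1 pharmacodynamic measurement after Baseline". For the safety population the same section says "it is defined as all subjects who receive at least 1 dose of study treatment", with no sampling condition.

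Time on treatment (5.2.5), compliance (5.2.6) and concomitant medication (5.2.7) are subsections of 5.2, and none names a population of its own. SAP 5.2.5, for example, says only: "The total number of days/weeks patients on treatment will be summarized". SAP 5.2.1 plans "Numbers and percentages of subjects enrolled, completed the treatment, and completed the study", also without naming a population.

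SAP 5.4 uses the safety population and lists what it covers: "All AEs, clinical laboratory results, physical examinations, vital signs, and 12-lead ECG readings data will be evaluated for safety". The matching sentence in Protocol 16.4.2 also includes concomitant therapy and procedures. SAP 5.4 leaves them out, and the only readable entry under SAP 5.7 (changes in methods) concerns the clinical assessment population.

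**The concern.** Exposure is normally read beside the adverse event tables: so many subjects, treated for so long, had these events. Here the two sides rest on different sets. A subject who takes the drug, has an adverse event and never returns for a blood draw adds to the adverse event numerator and denominator but nothing to exposure. If such subjects were treated only briefly, the exposure table makes treatment look longer than it was for everyone dosed, and its N does not match the N of the adverse event tables.

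Concomitant medication is a related loose end. The protocol treats it as safety data, its place in the SAP implies the pharmacodynamic population, and SAP 5.4.6 handles it under safety again for the lymphocyte follow-up period.

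**Working it through.** The plan gives no figure to reproduce here, so the check compares set definitions and then illustrates the size.

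**Step 1: the sets.**
- Safety = at least 1 dose.
- Pharmacodynamic (PD) = at least 1 dose and at least 1 post-baseline PD value.
- PD is therefore contained in Safety. The difference is dosed subjects with no post-baseline PD value.

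**Step 2: what counts as a PD value.** SAP 5.3 includes lymphocyte subsets, ALC and immunoglobulin isotypes. Because ALC counts, one post-baseline blood count with differential is enough.

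**Step 3: who would lack one.** The first scheduled post-baseline sample is at Week 4. A subject who leaves before then still has two chances to qualify:
- the Discontinuation and/or Withdrawal Visit, due within 2 weeks of the last dose, which collects hematology and subsets (Table 2 in both documents);
- the final Follow-Up Visit 4 weeks after the last dose, which collects both as well (Table 1 in both documents).

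The excluded group is therefore dosed subjects who never return for any blood draw. The documents give no estimate of their number.

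**Step 4: illustration.** These inputs are assumptions, apart from the planned 200 subjects (SAP 4): all 200 are dosed, *k* of them lack a PD value, those *k* have *e* = 2 weeks of exposure each, and the rest average *m* = 85 weeks.

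Mean on PD = *m*. Mean on Safety = [(200 − *k*)·*m* + *k*·*e*] / 200. Overstatement = (mean on PD / mean on Safety) − 1. Person-years left out = *k*·*e* / 52.18.

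| k | PD N | Mean on Safety (weeks) | Overstatement | Person-years left out |
|---|---|---|---|---|
| 0 | 200 | 85.0 | 0% | 0 |
| 2 | 198 | (198×85 + 2×2)/200 = 84.17 | 1.0% | 0.08 |
| 4 | 196 | (196×85 + 4×2)/200 = 83.34 | 2.0% | 0.15 |
| 10 | 190 | (190×85 + 10×2)/200 = 80.85 | 5.1% | 0.38 |
| 20 | 180 | (180×85 + 20×2)/200 = 76.70 | 10.8% | 0.77 |

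The last row is an extreme case. It takes the whole 10% discontinuation allowance in SAP 4 (200 × 0.10 = 20) and supposes that none of those subjects ever gives a sample. Varying *e* from 1 to 4 weeks changes little: 2.02% to 1.94% at *k* = 4, and 5.2% to 5.0% at *k* = 10.

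**Step 5: effect on adverse event results.** The readable text of SAP 5.4.1 plans incidence as subject counts and percentages on the safety population. It plans no exposure-adjusted rates, so no adverse event estimate uses the exposure denominator.

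**The case against.** The best defence is that the primary and secondary endpoints are pharmacodynamic, so describing baseline and exposure in the set that carries the main analysis is coherent. The protocol names no other population for exposure. SAP 5.1 promises an overview of the analysis populations, so the two counts should be visible. Adverse events leading to discontinuation or withdrawal are tabulated and listed on the safety population, so early leavers do not disappear from the report. The PD assignment is explicit only for baseline data and exposure; for compliance and concomitant medication it is inferred from where they sit.

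Most of this stands and limits the weight of the point. It justifies a baseline table on the PD population. It does not make that population the right denominator for exposure read beside safety data, and no readable text adds an exposure summary on the safety population.

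A reader might infer two stronger claims, and neither is supported:

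- *That the discontinuation rate is understated.* This needs SAP 5.2.1 to use the PD denominator. The opening sentence of 5.2 names baseline data and exposure, not disposition. Protocol 9.1 counts a subject as enrolled on signing consent, before any dose, so a table of enrolled subjects cannot sensibly be built on the PD set. The 10% in SAP 4 is a sample-size allowance, not a predicted disposition rate.
- *That those lost are mainly subjects who cannot tolerate the drug.* Protocol 11.2.4 has such subjects complete the final Follow-Up Visit before they are withdrawn, and that visit collects qualifying samples. An intolerant subject who follows the protocol is in the PD population.

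**Conclusion.** The point holds as a mismatch of populations. Exposure is explicitly on the pharmacodynamic set and adverse events on the safety set, and the difference is any dosed subject with no post-baseline PD value. That the same applies to compliance and concomitant medication is an inference from their position under 5.2; for concomitant medication it conflicts with Protocol 16.4.2.

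The effect is probably small and may be nil. Mean exposure is overstated only if such subjects exist and were treated for less time than the rest. The percentages shown depend on the assumed number lost and the assumed exposure times, none of which the documents give. No primary or secondary result and no adverse event percentage is affected. This is an improvement available at almost no cost, not a flaw that threatens a conclusion.

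**What to change.** Amend SAP 5.2 to say that:

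- exposure, compliance and concomitant medication (5.2.5 to 5.2.7) are summarised on the safety population;
- baseline characteristics are kept on, or also given for, the pharmacodynamic population if the two sets differ;
- the number of subjects in Safety but not in PD is reported;
- accounting of subjects (5.2.1) uses all enrolled subjects.

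The cost is a sentence or two of SAP text and a population flag in the affected tables. It needs no new data and no new method. If the two sets turn out to be identical, no exposure, compliance or concomitant medication result changes.

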5.2.1 Accounting of Subjects

Numbers and percentages of subjects enrolled, completed the treatment, and completed the study, along with reasons for discontinuing treatment and withdrawing from the study, will be presented.

5.2.2 Demographics and Baseline Disease Characteristics

Demographic data, including age (years), age category (18-19, 20-29, 30-39, 40-49, 50-55, and > 55), gender, country, race and ethnicity will be summarized. In addition, summary of height (cm), weight (kg), and BMI will be presented. A listing of demography will also be presented.

Baseline disease characteristics will also be summarized descriptively. Disease characteristics will include number of years since MS onset and diagnosis, [REDACTED]

CONFIDENTIAL

The information contained herein may not be used, disclosed, or published without the written consent of Biogen Idec MA Inc.

	Protocol 109MS310 An Open-Label Study to Assess the Effects of BG00012 on Lymphocyte Subsets in Subjects With RRMS	Final Version 1.0
---	---	--------------------------

5.2.3 Medical History and Previous MS Therapy

Medical history will be coded by MedDRA Version 19.1 or later and summarized, as number and percent of subjects, by system organ class (SOC) and preferred term (PT). Prior MS treatment history and baseline cardiac risk factors will also be summarized.

5.2.4 Protocol Deviations

Protocol deviations identified in the study will be listed.

5.2.5 Time on Study and Treatment

The total number of days/weeks patients on study will be summarized. Number of weeks the subject on the study will also be categorized into 12 week intervals and summarized. The total number of days subjects on study is calculated as

$$\text{Date of study end} - \text{date of first dose} + 1.$$

The total number of days/weeks patients on treatment will be summarized. Number of weeks the subject on treatment will also be categorized into 12 week intervals and summarized.

The time patients on temporary drug interruption will be excluded from the time on treatment calculation. Therefore, the total number of days subjects on treatment is calculated as

$$(\text{Date of last dose} - \text{date of first dose} + 1) - \text{total days of temporary dose interruption if any.}$$

For partial study or study treatment end date, if day is missing then impute the day to 30/31/28/29 depending on the month; if day and month are missing then impute the month and day to December 31st.

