7.2. Overall Study Duration and Follow-Up

The study period will consist of a Screening Visit within 4 weeks of Baseline, a Treatment Period of 96 weeks and a final Follow-Up Visit. Subjects will receive treatment for 96 weeks. The total duration of subject participation will be up to 104 weeks.

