10. DISCONTINUATION OF STUDY TREATMENT AND/OR WITHDRAWAL OF SUBJECTS FROM THE STUDY

10.1. Discontinuation of Study Treatment

A subject *must* permanently discontinue study treatment for any of the following reasons:

- The subject becomes pregnant. Study treatment must be discontinued immediately. Report the pregnancy according to the instructions in Section 15.4.1.
- The subject withdraws consent to continue study treatment.
- The subject experiences a medical emergency that necessitates permanent discontinuation of study treatment.
- The subject is unable to tolerate study treatment at 240 mg BID (see Section 11.2.4).
- The subject receives any concomitant medications not allowed by the protocol.
- The subject experiences any of the laboratory abnormalities requiring permanent discontinuation of treatment defined in [Table 3](#).
- The subject experiences more than 1 deviation of the same laboratory parameter that meets the threshold limits defined in [Table 3](#) at any time during the study.
- The subject experiences more than 2 different deviations of laboratory parameters that meet the threshold limits defined in [Table 3](#) at any time during the study. On a third occasion, the subject is required to discontinue dosing for the remainder of the study.
- If a subject has a lymphocyte count $<500/\text{mm}^3$ persisting for more than 24 weeks consecutively, study treatment must be temporarily withheld. Study treatment may be resumed after lymphocyte counts recover $>\text{LLN}$ on 2 consecutive occasions at least 4 weeks apart. If the subject develops a lymphocyte count $<500/\text{mm}^3$ on 1 occasion (confirmed by repeat testing) on resumption of study treatment, the subject must permanently discontinue study treatment and will continue protocol-required visits and assessments (see Section 11.3).
- If a subject's lymphocyte count remains $<\text{LLN}$ for 24 weeks consecutively after study treatment has been temporarily withheld due to lymphocyte count $<500/\text{mm}^3$ for more than 24 weeks, the subject must permanently discontinue study treatment.
- At the discretion of the Investigator for medical reasons or for noncompliance.

The reason for discontinuation of study treatment must be recorded in the subject's case report form (CRF).

Subjects who discontinue treatment may remain in the study and continue protocol-required tests and assessments.

CONFIDENTIAL

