11.3. Treatment Schedule for Subjects With Abnormal Lymphocyte Count

11.3.1. Schedule for Subjects With Lymphocyte Count $<500/\text{mm}^3$

Study treatment must be temporarily withheld when the laboratory value for lymphocyte count meets the threshold limits defined in [Table 4](#).

Table 4: Lymphocyte Count Criteria Requiring Withholding of Study Treatment

Laboratory Parameter	Laboratory Result	Required Action
Lymphocyte Count	$<500/\text{mm}^3$	
The Investigator should repeat the test as soon as possible. If re-test confirms that lymphocyte count is $<500/\text{mm}^3$, lymphocyte count should be closely monitored (at least every 4 weeks). If lymphocyte count is persistently $<500/\text{mm}^3$ for more than 24 weeks, study treatment must be temporarily withheld. If lymphocyte count is intermittently $<500/\text{mm}^3$ for more than 24 weeks, the Investigator should contact the Medical Monitor.
 
All assessments should be performed at the central laboratory.

While dosing is withheld, subjects will be followed every 4 weeks for 24 weeks, then every 12 weeks (**unless clinically indicated more often or at the Investigator's discretion**) until the lymphocyte count is $\geq\text{LLN}$ or for up to 48 weeks following drug discontinuation, whichever occurs sooner (see Lymphocyte Follow-Up in [Table 2](#)). If the lymphocyte count remains $<\text{LLN}$ for ≥ 24 weeks consecutively after the study treatment is withheld, the subject should be permanently discontinued from study treatment, and the Investigator should contact the Medical Monitor.

CONFIDENTIAL

[figure not shown]
The information contained herein may not be used, disclosed, or published without the written consent of Biogen MA Inc.

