2 STUDY DESIGN

2.1 Study Overview

This is an open-label, multicenter study to evaluate the effects of BG00012 on lymphocyte subtypes and Ig isotypes. Approximately 200 subjects were treated in approximately 100 sites in North America and Europe.

After the Screening Visit (up to 28 days) if required per local guidelines and if not already available within the previous 3 months, a magnetic resonance imaging (MRI) scan should be performed locally before starting therapy with BG00012 as per local guidelines. Subjects will then receive BG00012 treatment for 96 weeks (Treatment Period). Blood samples for lymphocyte subset analysis, as well as blood samples for the determination of each subject's complete blood count with differential, will be collected at Screening, Baseline (Day 1), and Weeks 4, 8, 12, 24, 36, 48, 60 (complete blood count [CBC only]), 72, 84 (CBC only), and 96. Clinical samples for the analysis of blood chemistries will be collected at Screening, Baseline (Day 1), and Weeks 4, 8, 24, 48, and 96. A post-treatment follow-up visit, at which safety assessments will be performed, will occur 4 weeks after the final dose of BG00012.

Subjects who temporarily withhold or permanently discontinue study treatment for any other reason than lymphopenia and have a lymphocyte count <LLN will continue protocol-required visits and assessments and will also be followed every 4 weeks for 24 weeks, then every 12 weeks (unless clinically indicated more often or at the Investigator's discretion) until the lymphocyte count is \geq LLN or for up to 48 weeks following drug discontinuation, whichever occurs sooner.

Subjects who develop a confirmed lymphocyte count of <500 cells/mm³ at any time during the study will be monitored every 4 weeks. If the lymphocyte count stays <500 cells/mm³ for 24 weeks, the subject will temporarily withhold study treatment. If the lymphocyte count does not recover to LLN within 24 weeks while study treatment is temporarily withheld, study treatment will be discontinued permanently.

CONFIDENTIAL

The information contained herein may not be used, disclosed, or published without the written consent of Biogen Idec MA Inc.

	
Protocol 109MS310 An Open-Label Study to Assess the Effects of BG00012 on Lymphocyte Subsets in Subjects With RRMS
	Final Version 1.0
---	---	--------------------------

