5.2.6 Treatment Compliance

The total number of study drug capsules taken by the subject will be summarized. The compliance through the date of last dose of study drug and the overall 96-week compliance who complete the study will be summarized. The percent compliance is defined as follows for each subject:

$$\text{Percent Compliance} = [(\text{total number of capsules taken}) / (\text{total number of capsules subject is expected to take})] *100$$

The total number of capsules that the subject expected to take is defined as the number of days the subject on the study drug multiplied by 4 (4 capsules is the expected number per day), except for the first week where 2 capsules a day is expected. The total number of capsules actually taken is calculated using total number of doses expected minus the missed doses.

CONFIDENTIAL

The information contained herein may not be used, disclosed, or published without the written consent of Biogen Idec MA Inc.

	Protocol 109MS310 An Open-Label Study to Assess the Effects of BG00012 on Lymphocyte Subsets in Subjects With RRMS	Final Version 1.0
---	---	--------------------------

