5.3.3 Lymphocyte analysis during lymphocyte follow-up period

Subjects who temporarily withhold, or permanently discontinue study treatment for any reason and have a lymphocyte count <LLN will continue protocol-required visits and assessments and will also be followed up every 4 weeks for 24 weeks, then every 12 weeks (unless clinically indicated more often or at the Investigator's discretion) until the lymphocyte count is \geq LLN or for up to 48 weeks following drug discontinuation, whichever occurs sooner.

In general, the lymphocyte follow-up analysis will include subjects who have at least one ALC < LLN during the treatment period and have at least one ALC value during the lymphocyte follow-up period. The lymphocyte follow-up period is defined as the time starting from the date of temporary dose interruption or study drug discontinuation. The start date of the lymphocyte follow-up period is defined as the start date of temporary dose interruption or the treatment end date. The last observed value collected on or prior to the date of temporary dose interruption or study drug discontinuation will be the reference point (lymphocyte follow-up baseline). Data that are collected during the lymphocyte follow-up period will be assigned to an appropriate visit by using the mid-point of the two visits windowing scheme. Visits will be mapped every 4 weeks for 24 weeks and then every 12 weeks afterward. The detailed windowing rule is available in [Appendix 2](#). Patients who have any post lymphocyte follow-up baseline values will be included in the analysis. ALCs collected during the lymphocyte follow-up period will be analyzed. The lymphocyte subsets and Ig isotypes observed obvious decline over time in the treatment period will also be explored.

The by-visit summary of actual value, change and percent change from the lymphocyte follow-up baseline in ALC during the lymphocyte follow-up period will be presented. The by-visit summary of actual value, change and percent change from the study baseline in ALC during the whole study period will also be presented. In addition, graphical display of median (Q1/Q3) of actual value in ALC in the whole study period will be presented; graphical display of median (Q1/Q3) of percent change from study baseline and lymphocyte follow-up baseline will be presented. The same analyses will be applied to selected lymphocyte subsets and Ig isotypes of interest.

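### SAP 5.2.5 subtracts every day of temporary interruption from time on treatment, with no limit to days before the last dose, so a withholding that is never resumed is taken out of real exposure

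*SAP*

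**What the plan says.** SAP 5.2.5 sets out the intent: "The time patients on temporary drug interruption will be excluded from the time on treatment calculation". The formula that follows takes last-dose date minus first-dose date plus 1, and subtracts "total days of temporary dose interruption if any". Weeks on treatment are then grouped into 12-week intervals. The section does not define the last-dose date for a subject whose withholding becomes permanent. It also does not say whether such a withholding remains a temporary interruption.

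The pathway that produces this situation is in both documents. Under Protocol 11.3.1 (Table 4), if the lymphocyte count is persistently below 500/mm³ "for more than 24 weeks, study treatment must be temporarily withheld". SAP 2.1, like Protocol 7.1, continues: "If the lymphocyte count does not recover to LLN within 24 weeks while study treatment is temporarily withheld, study treatment will be discontinued permanently". Protocol Table 3 has a shorter version for liver enzymes, creatinine and WBC: drug is withheld, and treatment ends if the value is still abnormal after at least 4 weeks.

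There is also a second lymphopenia stop. Under Protocol 10.1, if a subject has a confirmed count below 500/mm³ "on resumption of study treatment, the subject must permanently discontinue study treatment and will continue protocol-required visits and assessments".

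SAP 5.3.3 treats the start of an interruption and the end of treatment as two separate dates: "The start date of the lymphocyte follow-up period is defined as the start date of temporary dose interruption or the treatment end date". SAP 5.2.6 gives expected capsules as "defined as the number of days the subject on the study drug multiplied by 4", with 2 per day in the first week, and derives capsules taken as expected minus missed.

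**The concern.** The first term of the formula ends at the last dose; the subtracted term has no such end. When dosing resumes, the interruption lies inside the first term and the subtraction is right. When dosing never resumes, the interruption lies wholly after the last dose and was never in the first term. Subtracting it removes days on which drug was taken.

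The subjects exposed to this include those with severe, persistent, unrecovered lymphopenia. SAP 5.3.1 makes ALC below 0.5 × 10⁹/L for at least 6 months a named subgroup. Their reported exposure and 12-week category would be too low, and expected capsules and compliance in SAP 5.2.6 could be too.

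**Working it through.** The SAP gives a formula but no numerical result, so there is no stated figure to reproduce. The check compares two rules on worked cases, with the first dose on Day 1.

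- Literal rule (SAP 5.2.5): (last − first + 1) − all interruption days.
- Bounded rule: (last − first + 1) − interruption days between first and last dose.

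**Inputs**
- Withholding starts after 24 weeks below 500/mm³. Protocol 7.1 says 24 weeks and 11.3.1 says more than 24 weeks; 24 is used here. A later start moves the last dose but not the days subtracted, unless Week 96 intervenes.
- Terminal withholding lasts 24 weeks = 168 days (SAP 2.1, Protocol 7.1).
- Planned treatment is 96 weeks = 672 days (Protocol 7.2: "Subjects will receive treatment for 96 weeks").
- Table 3 withholding is taken at its 4-week minimum = 28 days.
- The last-dose date is the last dose taken, and the withholding stays recorded as temporary.

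**Check that the formula works when dosing resumes.** Withheld Days 200–227 (28 days), last dose Day 672: 672 − 28 = 644 under both rules. Withheld Days 253–336 (84 days), resumed, then stopped for a new count below 500/mm³ with last dose Day 420: 420 − 84 = 336 under both rules. The loss is zero in each.

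**Withholding never resumed**

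| Case | Last dose | Days withheld | Literal | Bounded | Loss |
|---|---|---|---|---|---|
| Count <500 from Week 4 | Day 196 | 168 | 28 | 196 | 168 (86%) |
| From Week 12 | Day 252 | 168 | 84 | 252 | 168 (67%) |
| From Week 24 | Day 336 | 168 | 168 | 336 | 168 (50%) |
| From Week 48 | Day 504 | 168 | 336 | 504 | 168 (33%) |
| From Week 60, cut off at Day 672 | Day 588 | 84 | 504 | 588 | 84 (14%) |
| Table 3 abnormality | Day 84 | 28 | 56 | 84 | 28 (33%) |

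A loss of 168 days is 2 × 84, so each full 24-week case drops two 12-week categories.

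**Compliance, if SAP 5.2.6 uses the same day count.** Expected capsules = 2 × 7 + 4 × (days − 7). For the Day 252 case:
- Bounded: 14 + 4 × 245 = 994.
- Literal: 14 + 4 × 77 = 322.
- Assume 5% of the capsules truly due were missed: 0.05 × 994 = 49.7.
- True compliance: (994 − 49.7)/994 = 95.0%.
- Literal compliance: (322 − 49.7)/322 = 84.6%.

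Under the same assumption, a true 95.0% reads 60.7% for onset at Week 4 ((98 − 38.5)/98) and 92.5% for onset at Week 48 ((1330 − 100.1)/1330). The summary of capsules taken falls too, from 944.3 to 272.3 in the Day 252 case.

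**Effect on the study mean.** The documents give no rate for the non-recovery branch. If 1% to 5% of 200 subjects (2 to 10) were in it, mean time on treatment would fall by 24 × 0.01 = 0.24 weeks to 24 × 0.05 = 1.2 weeks.

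**The case against.** The strongest reply is that this is a missing clarification rather than a wrong rule. The stated intent is sound, and days after the last dose have nothing to be excluded from. The error also needs two recording conventions together. If the last dose were recorded as the date of permanent discontinuation, the Day 252 case would give 420 − 168 = 252, which is correct. If the withholding were reclassified as discontinuation, it would give 252 − 0 = 252, also correct.

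Neither convention is stated in the documents. The first strains the ordinary meaning of last dose, which the protocol uses to time the discontinuation visit (within 2 weeks) and the final follow-up visit (4 weeks after). SAP 5.3.3 keeps interruption start and treatment end as separate dates and has no rule for one turning into the other. A programmer following the formula as written would get the wrong number. The dependence on recording does stand, and it is stated as an assumption below.

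Two further points stand. The Week 4 case is extreme: the protocol excludes subjects with a confirmed screening ALC at or below LLN, and Protocol 5.3.2 describes a gradual fall in mean counts. The effect on the study mean is also small under any plausible rate.

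**Conclusion.** The point holds. As written, the formula gives a wrong result for any interruption not followed by a further dose. In the lymphopenia non-recovery branch the loss is up to 168 days per subject. It is less when Week 96 cuts the withholding short, about 28 days for a terminal Table 3 withholding, and zero after resumed dosing. This assumes that the last-dose date is the last dose taken and that the withholding stays recorded as temporary. The number of affected subjects is not given.

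The effect is confined to the descriptive exposure summary and its 12-week categories, and to SAP 5.2.6 if it uses the same day count, which that section does not say. The primary endpoint, the MMRM and the sample size do not use time on treatment.

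Three stronger inferences are not supported:
- *Every subject stopped for lymphopenia loses 24 weeks.* Subjects who recover, resume and then stop under Protocol 10.1 lose nothing, and late withholdings lose less.
- *Compliance would exceed 100%.* SAP 5.2.6 defines capsules taken as expected minus missed, so the ratio cannot pass 100%. The error makes it too low.
- *Lymphopenia would appear to follow shorter treatment.* No visible SAP analysis relates lymphopenia to time on treatment. By-visit data are windowed from the first dose, and ALC subgroups are built from ALC values.

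**What to change.** In SAP 5.2.5:
- Limit the subtracted term to interruption days falling between the first dose and the last dose actually taken.
- Define the last-dose date as the date of the last dose taken.
- State that, for this calculation only, an interruption with no later dose counts as discontinuation from that date.

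In SAP 5.2.6, state that the number of days on study drug is this same count.

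The cost is a few sentences in the SAP and one condition in the exposure program. No new data are needed, results for resumed interruptions do not change, and no treatment rule is altered.
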